5.2 Exclusion Criteria

An individual who meets any of the following criteria will be excluded from participation in this study:

1) Target Disease Exceptions

- a) SBP < 115 mm Hg or > 180 mm Hg at screening or pre-randomization.
- b) Heart rate < 50 beats per minute (bpm) or > 120 bpm at screening or pre-randomization.
- c) Primary HF etiology attributable to either restrictive/obstructive cardiomyopathy, idiopathic hypertrophic or uncorrected severe valvular disease as defined by American Heart Association (AHA)/American College of Cardiology (ACC)/European Society of Cardiology (ESC) criteria.
- d) Patients with urinary/prostate disorders with urinary retention/significant bladder dysfunction or urinary incontinence.
- e) Inability to comply with the serial urine collection procedures.
- f) Pericardial tamponade or constrictive pericarditis.
- g) Left ventricular (LV) assist device or prior heart transplant.
- h) Hospitalized for acute decompensated HF in the previous month.
- i) New York Heart Association (NYHA) Class IV symptoms of HF.
- j) Hospitalized with acute coronary syndrome, coronary revascularization or acute myocardial infarction during the previous 90 days prior to screening.
- k) Have a history of a cerebral vascular accident (cerebrovascular accident [CVA] or stroke) or of a transient ischemic attack (TIA) during the previous 90 days prior to screening.
- l) Considered clinically unstable for any condition.
- m) Serious comorbid non-cardiovascular disease in which the life expectancy of the subject is < 3 months.
- n) Liver disease defined as history of cirrhosis with evidence of portal hypertension such as varices, or encephalopathy, or total bilirubin > 3 mg/dL (> 34.2 µmol/L) or significant elevation of liver enzymes (aspartate aminotransferase [AST], alanine aminotransferase [ALT] > 3 times the upper limit of normal).
- o) Prior solid organ transplant.

2) Prior/Concomitant Therapy

- a) Patients taking thiazides / metolazone or potassium-sparing diuretics (with the exception of spironolactone or eplerenone at doses \leq 50 mg/day which are allowed).

3) Physical and Laboratory Test Findings

- a) Have persistent abnormal serum electrolytes not resolved between screening and start of the study drug infusion, as defined by any of the following:
 - i) A sodium (Na⁺) concentration < 130 or > 145 mEq/L (mmol/L).
 - ii) A potassium (K⁺) concentration < 3.2 or > 5.5 mEq/L (mmol/L).
- b) Have severe anemia, as documented by a hemoglobin < 9 g/dL (< 5.59 mmol/L).

4) Allergies and Adverse Drug Reaction

- a) Any history of allergic reaction to components of BMS-986231, Captisol® or potassium acetate.
- b) Any history of allergic reactions to furosemide.

5) Other Exclusion Criteria

- a) Prisoners or participants who are involuntarily incarcerated. (Note: under certain specific circumstances a person who has been imprisoned may be included or permitted to continue as a participant. Strict conditions apply and Bristol-Myers Squibb's approval is required).
- b) Participants who are compulsorily detained for treatment of either a psychiatric or physical (e.g., infectious disease) illness.
- c) Participation in an investigational clinical drug study within 30 days or 5 elimination half-lives, (whichever is longer) prior to randomization.
- d) Prior participation and treatment in a study using BMS-986231.
- e) Alcohol beverage consumption within 6 hours prior to randomization.
- f) Body weight < 45 kg or ≥ 140 kg.
- g) Site personnel and their families.

Eligibility criteria for this study have been carefully considered to ensure the safety of the study participants and that the results of the study can be used. It is imperative that participants fully meet all eligibility criteria.

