Study participants will be admitted to the study facility the day before or on the treatment day, according to local practice and patient preferences. Assessment of symptoms and signs of HF, including body weight, vital signs and laboratory tests will be performed pre-dose (before start of infusion). On each treatment day, blood pressure and HR should be within the inclusion / exclusion criteria limits prior to study drug administration. The study drug infusion could start without waiting for the results of the laboratory assessments done in the morning of the treatment day at the study facility if the following criteria are met:

- The results of the laboratory assessment at screening / previous period are within ranges compatible with inclusion criteria,
- The study participant was medically stable with no signs of overt HF decompensation or deteriorating signs and symptoms of congestion and without change in medication since the screening visit / previous period.

If the laboratory tests (e.g. electrolytes, serum creatinine, estimated glomerular filtration rate (eGFR), hemoglobin, transaminases) on the morning prior to infusion, are not within inclusion and exclusion criteria limits, the study drug could be interrupted / discontinued after consultation with the Medical Monitor. The abnormalities should be corrected before the next treatment period.

Physical examinations, vital sign measurements, 12-lead ECG and urinary output will be performed at selected times throughout the dosing interval. Participants will be closely monitored for AEs throughout the study. Blood samples will also be collected at selected intervals after start of study drug administration for PK analysis and biomarkers.

Prior to start of the infusion, study participants will be asked to void and urine collected. A bladder scan can be performed to ensure adequate bladder emptying. Patients will be asked to void at least every 2 hours during the first 4 hours post-start infusion and before furosemide bolus, and at least hourly from 4 to 8 hours post-start infusion. At 8 hours after start of study drug infusion, just before study drug discontinuation, a void will be done, collected and recorded and a second bladder ultrasound can be performed to ensure adequate bladder emptying. Urine will be collected until 2 hours after the study drug discontinuation.

Discharge

[figure not shown]

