8 STUDY ASSESSMENTS AND PROCEDURES

- Study procedures and timing are summarized in the Schedule of Activities (Section 1.3).
- Protocol waivers or exemptions are not allowed.
- All immediate safety concerns must be discussed with the Medical Monitor immediately upon occurrence or awareness to determine if the participant should continue or discontinue treatment.
- Adherence to the study design requirements, including those specified in the Schedule of Activities (Section 1.3), is essential and required for study conduct.
- All screening evaluations must be completed and reviewed to confirm that potential participants meet all eligibility criteria before randomization. The investigator will maintain a screening log to record details of all participants screened and to confirm eligibility or record reasons for screening failure, as applicable.
- Procedures conducted as part of the participant's routine clinical management (eg, blood count) and obtained before signing of informed consent may be utilized for screening or baseline purposes provided the procedure meets the protocol-defined criteria and has been performed within the timeframe defined in the Schedule of Activities (Section 1.3).

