8.4.2 Vital Signs

Refer to Schedule of Activities (Section 1.3). Vital Signs (blood pressure and heart rate) will be recorded after the participant has rested quietly for at least 5 minutes in a supine position.

8.4.3 *Peripheral Oxygen Saturation*

Refer to Schedule of Activities (Section 1.3). Peripheral oxygen saturation will be recorded after the participant has rested quietly for at least 5 minutes in a supine position.

8.4.4 *Electrocardiograms*

Refer to Schedule of Activities (Section 1.3).

All ECG recordings must be performed using a standard high-quality, high-fidelity machine equipped with computer-based interval measurements and automated interpretation. Automated ECG intervals and HR will be captured or calculated, and changes of the T-wave and U wave morphology will be documented. ECG will be recorded after the participant has rested quietly for at least 5 minutes in a supine position.

8.4.5 *Continuous Cardiac Monitoring (Telemetry)*

Refer to Schedule of Activities (Section 1.3).

Continuous ECG monitoring will be performed to help monitor patient safety, primarily to detect ventricular and atrial arrhythmias. The site will follow their normal operating procedures established for ECG monitoring by trained staff. Clinically significant findings from the monitoring will be recorded as AEs and SAEs per investigator's decision, and at the investigator's discretion the infusion may be discontinued for clinically significant arrhythmias.

8.4.6 *Clinical Safety Laboratory Assessments*

Investigators must document their review of each laboratory safety report. Subjects will have laboratory tests performed as described in the following sections. A central/local laboratory will perform the analyses and will provide reference ranges for these tests.

Laboratory assessments for screening

The following laboratory tests will be performed as part of the screening evaluation. Results will be recorded in the study eCRF.

Hematology

- Hemoglobin
- Hematocrit
- White blood cell count and differential
- Platelet count

Serum Chemistry

- Aspartate Aminotransferase (AST, SGOT)
- Alanine Aminotransferase (ALT, SGPT)
- Blood Urea Nitrogen (BUN)
- Electrolytes
 - Sodium
 - Potassium
- Serum Creatinine (Scr)

- eGFR by equation used locally

Other Analyses

- BNP or NT-pro BNP (according to local lab availability) will be performed at screening.
- Pregnancy test (WOCBP only: screening, pre-dose (before start of infusion) in each treatment period).

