On each treatment day, the study drug infusion could start without waiting for the results of the laboratory assessments done in the morning of the treatment day at the study facility if the following criteria are met:

- The results of the laboratory assessment at screening / previous period are within ranges compatible with inclusion criteria.
- The study participant was medically stable with no signs of overt HF decompensation or deteriorating signs and symptoms of congestion and without change in medication since the screening visit / previous period.

Laboratory Assessments During Study

The following laboratory tests will be performed and submitted to the Laboratory or Sponsor designated vendors for analysis as per the Study Assessment and Procedures.

Analyses		Timing
Hematology	
 • Hemoglobin • Hematocrit • White blood cell count, including differential • Platelet count 	H0 (before start of infusion), H4 and H8 on each treatment day
Serum Chemistry	
 • Aspartate Aminotransferase (AST, SGOT) • Alanine Aminotransferase (ALT, SGPT) • Total bilirubin • Serum Creatinine (Scr) • eGFR • BUN 	H0 (before start of infusion), H4 and H8 on each treatment day
	
 • Electrolytes: Na, K, Creatinine, eGFR • Bicarbonate, free water clearance 	H0 (before start of infusion), H4, H5, H6, H7, H8 on each treatment day
Furosemide	
 • Furosemide plasma concentration 	Please refer to Table 7
Urinalysis	
 • Fractional excretion of sodium • Fractional excretion of potassium • Urine Na, K, bicarbonate, creatinine, urea, phosphate, chloride, urine albumin-to-creatinine ratio (uACR) • Furosemide urinary concentration • Exploratory urinary biomarkers: including but not limited to urine kidney injury molecule-1 (KIM1) 	Please refer to Table 8

The detailed methods for specimen collection, handling, processing, shipping, and storage will be supplied in the Investigator's Laboratory Manual provided by the Laboratory.

8.4.7 *Suicidal Risk Monitoring*

Not applicable.

8.4.8 *Imaging Safety Assessment*

Any incidental findings of potential clinical relevance that are not directly associated with the objectives of the protocol should be evaluated and handled by the investigator as per standard medical/clinical judgment.

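### The bilirubin exclusion gives two different limits as if they were one (3 mg/dL is 51.3 µmol/L, not 34.2), and no bilirubin test is scheduled at screening

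*Protocol*

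**What the plan says.** Protocol Section 5.2, exclusion 1) n), defines excluded liver disease by a history of cirrhosis with signs of portal hypertension, by raised bilirubin, or by AST or ALT above three times the upper limit of normal. The bilirubin part reads "encephalopathy, or total bilirubin > 3 mg/dL (> 34.2" µmol/L). The section closes with "It is imperative that participants fully meet all eligibility criteria".

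Section 8.4.6 introduces the screening panel with "The following laboratory tests will be performed as part of the screening evaluation". Its serum chemistry list has AST, ALT, BUN, sodium, potassium, creatinine and eGFR. Total bilirubin is not on it. It first appears in the on-study chemistry, timed "H0 (before start of infusion), H4 and H8 on each treatment day".

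Section 4.1 (Treatment Day), repeated in Section 8.4.6, allows dosing ahead of those results: "The study drug infusion could start without waiting for the results of the laboratory assessments done in the morning of the treatment day", provided that "The results of the laboratory assessment at screening / previous period are within ranges compatible with inclusion criteria" and the participant is medically stable with no change in medication. Section 8 requires the following: "All screening evaluations must be completed and reviewed to confirm that potential participants meet all eligibility criteria before randomization". It also says that routine-care results obtained before consent "may be utilized for screening or baseline purposes provided the procedure meets the protocol-defined criteria" and are recent enough.

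**The concern.** A limit printed in two units should be one limit. If the two figures differ, whether a patient is eligible depends on the unit in which the local laboratory reports, and nothing in the documents says which figure governs. If 3 mg/dL was intended, a site working in µmol/L would wrongly exclude patients. If 2 mg/dL was intended, a site working in mg/dL would admit patients whom the sponsor meant to keep out. Agreement between sites would not settle it, because they could all be applying the unintended limit.

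The second issue is whether the criterion can be checked in time. If bilirubin is not measured at screening and dosing need not wait for the H0 sample, this part of a safety exclusion can go unchecked until after first exposure.

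**Working it through.** **Inputs**
- Printed pair: 3 mg/dL and 34.2 µmol/L (Protocol 5.2, exclusion 1) n)).
- Molar mass of bilirubin, C33H36N4O6. This is an assumption, as the documents do not give it: 33 × 12.011 + 36 × 1.008 + 4 × 14.007 + 6 × 15.999 = 584.67 g/mol.

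**Conversion**
- µmol/L = mg/dL × 10,000 / molar mass. The factor is 10,000 / 584.67 = 17.10.
- From the mg/dL figure: 3 × 17.10 = 51.3 µmol/L. The printed 34.2 is not reproduced.
- From the µmol/L figure: 34.2 / 17.10 = 2.00 mg/dL.
- Factor implied by the printed pair: 34.2 / 3 = 11.4, which would need a molar mass of 10,000 / 11.4 = 877 g/mol. That is not bilirubin.

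**Could rounding or the choice of factor explain it?**
- Values that round to 3 mg/dL run from 2.5 × 17.1 = 42.8 to 3.5 × 17.1 = 59.9 µmol/L. The printed 34.2 lies outside.

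| Factor | 3 mg/dL in µmol/L | 34.2 µmol/L in mg/dL |
|---|---|---|
| 17.0 | 51.0 | 2.01 |
| 17.1 | 51.3 | 2.00 |
| 17.2 | 51.6 | 1.99 |

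**Size of the gap**
- 51.3 − 34.2 = 17.1 µmol/L, or 1.0 mg/dL; 51.3 / 34.2 = 1.50.

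**Comparison within the same section**
- Exclusion 3) b) gives hemoglobin 9 g/dL as 5.59 mmol/L. With an assumed factor of 0.6206, 9 × 0.6206 = 5.585, which agrees. The section's other converted limit is therefore a true equivalent, and the bilirubin bracket should be read as meant the same way.

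**Timing of the bilirubin check**
1. The Section 8.4.6 screening list has no bilirubin, and the laboratory row of Table 1 points to that section.
2. The first scheduled bilirubin is at H0 on the first treatment day.
3. In Period 1, the laboratory condition for starting before H0 results rests on the screening panel, so it can be met with no bilirubin value on file. Read literally, that condition names only the inclusion criteria, and bilirubin is an exclusion criterion.
4. In Period 2 the previous period supplies bilirubin values, so the gap concerns first dosing.

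**The case against.** The unit mismatch has no good defence; the case on the other side concerns its consequences and the screening gap.

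- **Later safeguard.** Section 4.1 lets the study drug be interrupted or stopped, after consulting the Medical Monitor, if morning results fall outside the eligibility limits. Bilirubin is in the H0 panel, and the tests named there are only examples, so it can be covered. This limits the harm, but the step is discretionary and acts after randomization and exposure.
- **A value is implied.** Section 8 requires all eligibility criteria to be confirmed before randomization and forbids waivers, so a careful site would obtain a bilirubin value or use a routine-care one. This is fair: the protocol does not license skipping the check. But it schedules no test that would supply the value, and routine-care results are permitted rather than required.
- **Another reading of the criterion.** Bilirubin could be taken to qualify known liver disease rather than stand alone. The wording allows this, and it would weaken the screening point. It leaves the unit error untouched.
- **Small practical effect.** SAP Section 6.2 names two sites, Glasgow and London. If both report in µmol/L (an assumption), both would apply 34.2, the lower limit, and no difference between sites would arise. Patients are stable, NYHA Class IV is excluded, and AST and ALT are screened. All of this bears on how many patients are affected, not on whether the criterion is wrong as printed.

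**Conclusion.** The concern holds. The two bilirubin limits differ by 17.1 µmol/L (1.0 mg/dL), a factor of 1.5, and the documents do not show which was intended. The only outside input is bilirubin's molar mass, and the result does not change over any plausible conversion factor. The screening point also holds, as the secondary one: the scheduled screening tests cannot confirm this criterion, and first dosing may precede the first scheduled bilirubin result.

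The documents give no frequency of bilirubin above 34.2 and up to 51.3 µmol/L in stable HFrEF patients, so the number affected cannot be estimated and may be zero of about 20. This is an eligibility and safety correction that should be made. It has no shown effect on sample size, power, the per-protocol set or the primary analysis.

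**What to change.** State one limit correctly in both units in exclusion 1) n). The choice is the sponsor's: either above 3 mg/dL (51.3 µmol/L) or above 2 mg/dL (34.2 µmol/L).

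Add total bilirubin to the screening serum chemistry in Section 8.4.6, run on the sample already taken for AST and ALT, so that the criterion is checked before randomization.

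The cost is one corrected number and one extra analyte on an existing sample, with no added visit or blood draw. A minor amendment covers both.

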5.3 Lifestyle Restrictions

5.3.1 Meals and Dietary Restrictions

Study participants will be asked to eat their usual diet, but it should remain similar for the 3 days prior to the infusion. Patients should keep a 3-day diet diary to record what they consume. During the infusion, study participants will be given up to 200 mL / hour as fluid intake, as tolerated. Urinary output will be collected every 2 hours in the first 4 hours and then hourly from 4 hours to 8 hours after start of infusion.

On each treatment day standardized meals and snacks will be served. No fasting is required the evening prior to each treatment day.

5.3.2 Caffeine, Alcohol and Tobacco

Study participants will avoid alcohol in the 6 hours prior to infusion start and caffeine in the 12 hours prior to infusion start and during the stay in the clinic. Smoking is not allowed during the stay in the clinic.

5.4 Screen Failures

Screen failures are defined as participants who consent to participate in the clinical study but are not subsequently randomized. A minimal set of screen failure information is required to ensure transparent reporting of screen failure participants, to meet the Consolidated Standards of Reporting Trials (CONSORT) publishing requirements, and to respond to queries from regulatory

authorities. Minimal information includes date of consent, demography, screen failure details, eligibility criteria, and any serious AEs.

5.4.1 *Retesting During Screening or Lead-In Period*

Participant Re-enrollment: This study permits the re-enrollment of a participant that did not initially meet Inclusion/Exclusion criteria (i.e., participant has not been randomized). If re-enrolled, the participant must be re-consented.

Laboratory parameters and/or assessments that are included in [Table 1](#), Screening Procedural Outline may be repeated in an effort to find all possible well-qualified participants. Consultation with the Medical Monitor may be needed to identify whether repeat testing of any particular parameter could allow for the patient to be randomized.

6 TREATMENT

Study treatment is defined as any investigational treatment(s), marketed product(s), placebo or medical device intended to be administered to a study participant according to the study randomization or treatment allocation.

Study treatment includes both Investigational [Medicinal] Product (IP/IMP) and Non-investigational [Medicinal] Product (Non-IP/Non-IMP) and can consist of the following:

An investigational product, also known as investigational medicinal product in some regions, is defined a pharmaceutical form of an active substance or placebo being tested or used as a reference in a clinical study, including products already with a marketing authorization but used or assembled (formulated or packaged) differently than the authorized form, or used for an unauthorized indication, or when used to gain further information about the authorized form.

In this study the investigational products are BMS-986231 for injection and placebo.

Other medications used as support or escape medication for preventative, diagnostic, or therapeutic reasons, as components of the standard of care for a given diagnosis, may be considered as non-investigational products.

In this study, the required potassium acetate used as a buffer for BMS-986231 infusions and furosemide are considered non-investigational products.

Study medication will be prepared by an unblinded pharmacist (or appropriate designee) on Day 1 of each period (treatment day), at time of randomization in the first period and before start of the infusion for the second period. Detailed instructions for preparing, reconstituting, and handling of BMS-986231 and placebo, as well as infusion setups, instructions for labeling individual infusion bags after they are prepared, and information on dosing solution stability are provided in the Study Pharmacy Manual.

Table 4: Study Treatments for CV013-034

Product Description / Class and Dosage Form	Potency	IP/Non-IMP	Blinded or Open Label	Packaging / Appearance	Storage Conditions (per label)
BMS-986231 For Injection ^a	240 mg/vial	IP	Blinded	Vial(s) in a carton	Refer to the label on container and/or pharmacy manual
Furosemide	10 mg/mL	Non-IMP	Open Label	TBD	Refer to the label on container and/or pharmacy manual
Placebo	Not Applicable	IP	Blinded	TBD	Refer to the label on container and/or pharmacy manual
Potassium Acetate Injection, USP ^b	2 mEq/mL	Non-IMP	Open Label	Vial(s) in a carton.	Refer to the label on container or package insert / summary of product characteristics

^a BMS-986231 for infusion contains active pharmaceutical ingredient BMS-986231 240 mg/vial formulated with Captisol® 3405 mg/vial

^b Potassium Acetate Injection may be supplied by BMS centrally (ex-US sites) or through site sourcing procedures. It is used as a buffer for BMS-986231 infusion (1 mEq potassium per 100 mL of reconstituted BMS-986231 further diluted for infusion).

